**1. Hypothesis:**

Intra articular injections with autologous platelet rich plasma (PRP) will improve symptoms, recovery time, and imaging appearance using delayed gadolinium enhanced MRI of cartilage (dGEMRIC) or Non-contrast MRI in patients suffering from stable juvenile osteochondritis dissecans of the knee when compared with conservative therapy.

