Battaglia et al recently reported the outcomes of injection of PRP for OA of the hip. Twenty patients, with a mean age of 52 years, who presented symptomatic OA of the hip were treated with a total of 3 intrarticular injections of PRP. Patients were prospectively evaluated at 1, 3, 6, and 12 months follow up. All patients had significantly improved clinical symptoms. No major complications or adverse events occurred at the moment of injection or in the follow-up period. Ten patients reported a slight pain during or after the injection, which spontaneously resolved in 1 or 2 days [30].

Gillis et al evaluated autologous chondrocyte transplantation in patients with full thickness chondral lesions of the knee utilizing dGEMRIC to indirectly quantify the GAG content of cartilage at the site of transplant, adjacent to the site of transplant, and distant to the site of transplant. The study demonstrated that GAG levels in grafts that had been implanted at 12 months or greater had GAG levels comparable to adjacent and remote cartilage. [31]

Typically, patients with Juvenile Osteochondritis Dessicans will heal without treatment within a 12 month period, therefore it was recently decided that the research dGEMRIC MRI would be performed 6 months from the time of the consent instead of 12 months. [32]

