#### **4. Research Methods**

We propose a randomized controlled clinical trial in children (aged 10-17) with osteochondritis dissecans (OCD) comparing the use of platelet-rich plasma (PRP) therapy and conventional therapy compared to conventional therapy alone.

The goal of this research is to test the hypothesis that intra articular injections with autologous PRP will improve symptoms, recovery time, and imaging appearance using delayed gadolinium enhanced MRI of cartilage (dGEMRIC) or MRI diagnostic cartilage sequence findings in patients suffering from stable juvenile OCD of the knee when compared to conservative therapy. Specifically, we aim to determine whether intra-articular platelet injections when compared to conservative therapy over time, lead to greater cartilage healing (measured by gadolinium accumulation or measured by healing on Non-contrast MRI, utilizing the DiPaola classification system), improvement in pain, improvement in performance of activities of daily living, improvement in sport performance, and improvement in overall function and symptom reduction.

Finally, we aim to determine if dGEMRIC findings or MRI diagnostic cartilage sequence findings on imaging studies correlate with measures of functional recovery and symptom reduction.

All protocol procedures other than patient randomization, PRP injections, and the 6 month dGEMRIC or Non-Contrast MRI are considered routine standard of care procedures. These three procedures are being conducted for research purposes in this study.

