[http://www.sportsmed.org/uploadedFiles/Content/Medical\\_Professionals/Research/Grants/IKDC\\_Forms/Pedi-IKDC%20Form.pdf](http://www.sportsmed.org/uploadedFiles/Content/Medical_Professionals/Research/Grants/IKDC_Forms/Pedi-IKDC%20Form.pdf)

Clinical follow up will also be performed following injections or the commencement of conservative therapy at 6 weeks, 12 weeks, 6 months, 9 months, and 12 months by [name]/[name] or their colleagues on the CHCO main campus or one of the following satellite locations (South, Parker, Centennial, Uptown/St Joseph's or Broomfield). The clinical findings documented will include presence or absence of a joint effusion, overall range of motion, presence or absence of joint line tenderness and positive or negative Wilson's test 6 week follow up for both groups will also include radiographic evaluation, which is standard of care. If

the patient is clinically or radiographically improving, physical therapy will be started as standard of care, following the same treatment protocol initially with closed kinetic chain, non-impact exercises. Patients will then slowly return to impact activities as tolerated over 3 to 4 months.

A patient Timeline of Activity has been created for each arm of the study (see two attachments). The Timeline describes the weekly and monthly events that will occur during this study and can be handed to the patient following the consent and randomization process.

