#### **Research MRI utilizing Non-contrast MRI**

A Non-contrast MRI will be performed in the standard manner. Upon arriving to the radiology department for the MRI, a pregnancy test will be administered for all female participants of child bearing potential. An institutional MRI screening form will be given to each patient and parent and reviewed with the MRI technologist. If there is any retained metal (pacemaker, metallic bb, orthopedic hardware), MRI will not be performed.

Table 3 – Patient Schedule of Assessment												
Procedure Step		Pre-Screen Visit	Week 1 +/- 10 d	Week 2 +/- 10 d	Week 3 +/- 10 d	Week 4	Week 5	Week 6 +/- 1wk	Week 12 +/- 1wk	Month 6* +/- 1wk	Month 9 +/- 1wk	Month 12 +/- 2wk
Non-contrast MRI, MRI with and without contrast, or dGEMRIC for OCD lesion ( standard of care )	X A								X R			
Initial & Follow-up x-rays dependent on symptoms ( standard of care )	X							X D	X D	X D	X D	
Informed Consent ( research )	X B											
Inclusion / Exclusion Criteria confirmation ( research )		X R										
Patient Reported Outcomes IKDC, KOOS-child ( research )		X R					X R	X R	X R	X R	X R	
Randomization ( research )		X										
Compliance Survey ( research )		X R	X R	X R	X R	X R	X R					
Physical exam ( research for PRP arm patients weeks 1, 2, & 3 and standard of care visits for both treatment arms for weeks 6, 12 and months 6, 9, 12)		X C	X C	X C			X	X	X	X	X	
Blood draw & processing using the Harvest PRP kit( research )		PRP only	PRP only	PRP only								
Autologous PRP Injection ( research )		PRP only +/- 7days	PRP only +/- 7days	PRP only +/- 7days								
Hinged Brace in extension for 6 wks ( standard of care )		X	X	X	X	X	X					

X = occurs for both patient groups;

A = Standard of care visit to pre-screen for minimal inclusion criteria; all patients will undergo the same standard of care MRI procedure

B = Patient consenting can occur at either the initial screening visit, or when given the option to take the consenting material home for review they will be consented at their 2nd visits if they choose to enroll in the study.

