### **9. Summarize Knowledge to be Gained**

The study is designed to objectively evaluate whether intra articular injections with autologous platelet rich plasma (PRP) will improve recovery time and cartilaginous healing in patients suffering from (stable) osteochondritis dissecans of the knee when compared with conservative therapy.

Radiation-free MRI with dGEMRIC or a non-contrast MRI will be used to assess osteochondritis dissecans healing by comparing mean T1 values obtained at the site of pathology on initial and follow up exams in comparison to mean T1 values of cartilage adjacent to the site of pathology and distant to the site of pathology on initial and follow up imaging and/or interval change in DiPaolo score with Non-contrast MRI.

The benefit of more rapid healing of osteochondritis dissecans is reduction in morbidity, as well as potentially eliminating surgical treatment. Dissemination of results will occur via publication in a peer reviewed journal in the fields of radiology, orthopedic surgery, or both.

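### Recovery time is a stated target of the trial, but the plan defines no time-to-recovery endpoint and no analysis estimates one

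*Combined protocol and SAP*

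**What the plan says.** Recovery time is named in three places.

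- Section 1 (Hypothesis) says the injections "will improve symptoms, recovery time, and imaging appearance using delayed gadolinium enhanced MRI of cartilage (dGEMRIC) or Non-contrast MRI", relative to conservative therapy.
- Section 4 (Research Methods) repeats this as the objective: "The goal of this research is to test the hypothesis that intra articular injections with autologous PRP will improve symptoms, recovery time, and imaging appearance".
- Section 9 (Summarize Knowledge to be Gained) gives the purpose: "The study is designed to objectively evaluate whether intra articular injections with autologous platelet rich plasma (PRP) will improve recovery time and cartilaginous healing".

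Section 2 (Specific Aims) lists the endpoints. Aim 1 uses T1GD on dGEMRIC or change in DiPaola grade. Aim 2 uses the KOOS-child pain, ADL and sports subscales and the pedi-IKDC. Aim 3 correlates imaging with those scores.

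Two other passages bear on speed. Preliminary Studies says "Typically, patients with Juvenile Osteochondritis Dessicans will heal without treatment within a 12 month period", and gives this as the reason for moving the research MRI from 12 months to 6. The section on surveys and clinical assessments says "The clinical findings documented will include presence or absence of a joint effusion, overall range of motion, presence or absence of joint line tenderness", together with Wilson's test. These are recorded in both arms at 6 weeks, 12 weeks, and 6, 9 and 12 months. No planned analysis uses them.

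**The concern.** The hypothesis has three parts. Symptoms are covered by KOOS-child and pedi-IKDC, and imaging by T1GD or DiPaola grade. Recovery time is the only part without an endpoint. It is not a stray phrase: the protocol expects most untreated patients to heal within a year, and section 9 presents faster healing as the benefit.

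What is at stake is the conclusion. If no result is named in advance as the measure of recovery speed, the choice can be made after the data are seen. Patients and parents know their assignment, so a loosely supported claim of faster recovery based on reported scores would be hard to defend. A claim of no effect on recovery time would be equally unsupported.

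**Working it through.** The documents give no figure for recovery time, so there is none to reproduce. The check traces the term through the plan, then asks what the nearest analyses could show.

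**1. Tracing the term.** It appears in sections 1, 4 and 9. It does not appear in the three aims, or in the list in section 4 that spells out what the study will determine. Table 3 has no row for a recovery date. No section defines recovered status, a time origin or censoring. Return to impact activity is described as part of care, not as an outcome.

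**2. The planned tests.** The Bonferroni divisors give the counts: 0.05/3 = 0.017 (Aim 1), 0.05/12 = 0.004 (Aim 2) and 0.05/4 = 0.0125 (Aim 3). That is 3 + 12 + 4 = 19 tests at most. The outcomes are T1GD at two visits, four scores at five visits, and 6-month T1GD (with a reference to DiPaola change in Aim 3). None is a duration.

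**3. What Aim 2 can show.** Let d(t) be the difference in mean score, PRP minus conservative, at visit t. The interaction test asks whether d(t) changes across 6 weeks, 12 weeks, and 6, 9 and 12 months.

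- If it is rejected, the gap changes. It may widen, narrow or cross zero, and no duration is estimated.
- If PRP patients gain by week 6 and keep the same advantage, d(t) = c at all five visits and the true interaction is zero.
- The step-down treatment effect would then test c, which is a difference in level. The model lists no baseline visit and its only covariate is age, so a chance baseline imbalance could produce the same c.

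**4. What the MRI can show.** Imaging is read at the initial scan and at 6 months. For each patient this gives status at 6 months, not the date of healing.

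**5. What the recorded clinical signs could add.** Assume 6, 9 and 12 months are weeks 26, 39 and 52.

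- The intervals are 6, 12 − 6 = 6, 26 − 12 = 14, 39 − 26 = 13 and 52 − 39 = 13 weeks, before visit windows.
- Planned examinations number 24 × 5 = 120. With the expected loss of up to two patients per arm, completers contribute 20 × 5 = 100.
- For power, assume 1:1 allocation, two-sided alpha 0.05 and exactly known event times (Schoenfeld): power = Φ(√D × ln HR / 2 − 1.96), where D is the number of events.
- If all 24 recover and HR = 2: √24 × 0.693 / 2 = 1.698; 1.698 − 1.960 = −0.262; Φ(−0.262) = 0.40.

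| HR | Power, D = 24 | Power, D = 20 |
|---|---|---|
| 1.5 | 0.17 | 0.15 |
| 2 | 0.40 | 0.34 |
| 3 | 0.77 | 0.69 |
| 4 | 0.92 | 0.87 |

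At HR = 2, 80% power needs about 66 events.

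**The case against.** The best reply is that Aim 2 already covers speed. It compares the arms on improvement over follow-up, its analysis section is headed as concerning functional recovery, and it tests whether trajectories differ for four scores. The 6-month MRI was also placed early so that a difference in healing progress might still be visible. Both points stand. A reader might infer that the trial is silent on speed of recovery, and the documents do not support that. The evidence is indirect and undesignated, but it exists.

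Other strong readings also fail.

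- **Favourable visits could be picked.** The plan has no per-visit tests. It has an interaction test followed by main effects, all at 0.004.
- **Radiographic recovery would be ascertained unevenly.** Table 3 does say "Initial & Follow-up x-rays dependent on symptoms". But the clinical assessments section includes radiographs for both groups at 6 weeks, and the treatment schedules list x-rays at follow-up visits. The sections differ, so uneven ascertainment is not established.
- **Speed is the main benefit PRP could show.** Section 9 also names the possibility of avoiding surgery.
- **A formal time-to-recovery endpoint is required.** One built on the recorded signs has real problems. Entry does not require those signs, so some patients could count as recovered at week 6. Table 3 schedules the week 1 to 3 examinations for the PRP arm only, and the examination promised for all subjects has no stated time. Follow-up is counted from the injections or from the start of conservative therapy, so the origin may differ by arm. Examiners are not stated to be blinded. Conservative-arm patients who need surgery leave the study.

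**Conclusion.** The point holds as a mismatch between stated objective and plan. Recovery time is in the hypothesis, goal and purpose, but it has no defined endpoint and none of the up to 19 tests estimates it. The Aim 2 trajectories and the 6-month MRI are relevant to speed, but they do not yield a time to recovery, and the plan does not name either as its measure.

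The trial therefore cannot answer the recovery-time question directly. That does not make it uninformative about speed, and it does not touch the Aim 1 endpoint on which power was calculated. The conclusion rests on the text alone. The power figures are illustrations under the assumptions shown, and they serve only to show that a time-to-event analysis in 24 patients would be descriptive unless the effect were very large. The wording should be settled before the blind is broken, because it determines what the trial may conclude.

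**What to change.** Choose one of two wording changes.

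1. Delete recovery time from sections 1, 4 and 9, and limit conclusions to imaging status at 6 months and scores at the scheduled visits.
2. State in advance that the KOOS-child and pedi-IKDC trajectories of Aim 2 are the measure of speed of recovery, and that no claim of shorter time to recovery will go beyond them. Include the baseline scores, which are already collected in both arms, so that an early gain held constant can be told apart from a baseline difference.

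Optionally, add a visit-based analysis of time to recovery from the recorded clinical signs, labelled descriptive. It would need a pre-specified definition of recovery, one time origin for both arms, a baseline examination in both arms, and rules for patients without the signs at entry and for those withdrawn for surgery.

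The cost is protocol and analysis-plan wording and a narrower stated objective. The optional analysis would use mostly existing data, would need the baseline examination secured in both arms, and would have low precision.
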